Liver Fibrosis Evaluation Using Ultrasound Shear Wave Imaging

NCT03637959

March 29, 2019

IRB Minimal Risk Protocol Template

General Study Information

Principal Investigator: [name]

Study Title: Liver Fibrosis Evaluation Using Ultrasound Shear Wave Imaging

Protocol version number and date: March 29, 2019

Purpose

Hypothesis: Liver stiffness measured by Ultrasound Shear Wave Imaging is correlated with liver stiffness measured by MRE (Magnetic Resonance Elastography).

Aims, purpose, or objectives: Liver stiffness measured by MRE can be used for noninvasive liver fibrosis staging. However, MRE is expensive and not widely available. This study will evaluate the efficacy of liver stiffness measured by ultrasound for fibrosis staging, using clinically indicated MRE as the gold standard. A secondary aim is to measure the fat content of liver using ultrasound and to study the correlation of liver fat and fibrosis.

Background (*Include relevant experience, gaps in current knowledge, preliminary data, etc.*):

Liver fibrosis/cirrhosis afflicts hundreds of millions of patients worldwide and 900,000 Americans. Liver biopsy, currently the gold standard for the diagnosis of liver fibrosis, is invasive and may occasionally cause significant complications, which limits the screening of at-risk populations, treatment monitoring, and follow-up. Liver stiffness measured by MRE (Magnetic Resonance Elastography) is used clinically at Mayo for non-invasive liver fibrosis staging. In MRE, small mechanical vibrations are applied at body surface and shear waves (mechanical waves due to vibration perturbation) thus introduced in liver is detected by Magnetic Resonance Imaging and used to calculate the stiffness of liver. However, MRI is expensive and not widely available. In this study, we will evaluate the feasibility of using ultrasound to detect shear waves introduced by small mechanical vibration for liver fibrosis staging. We expect that this new method will have better penetration compared to existing ultrasound elastography techniques, and therefore has more reliable measurements in obese patients. This is an important advantage considering prevalence of obesity in USA.

Subject Information – charts, records, images, or specimens are considered ‘subjects’

Target accrual: *Proposed number of subjects to be included in your study at your site. “Subjects” may include Mayo Clinic charts, records, or specimens, and/or charts, records, or specimens received at Mayo Clinic from external sources for collaborating analysis by the investigator under this IRB application:*

Subject population: 325 patients (with clinically indicated liver MRE) and healthy volunteers.

Inclusion Criteria: Both male and female healthy volunteers or patients who are scheduled for clinically indicated liver MRE for fibrosis staging, age 18 to 80.

Exclusion Criteria: subjects lacking capacity to consent, or subjects with unreliable ultrasound or MRE measurements. Pregnant women will be excluded. Women of child bearing potential will be asked by our study coordinator if they are pregnant. If not sure, a urine pregnancy test will be given to screen the subject at no cost to the subject.

Will a Certificate of Confidentiality be obtained? *If yes, provide an explanation.*

No.

Study Design

Methods: *Describe, in detail, the research activities that will be conducted under this protocol:*

Study on patients and volunteers will take place in the Radiology department using the GE Logiq E9 scanner (FDA approved), GE Logiq E10 (FDA approved), and the Verasonics ultrasound scanner. The first ultrasound scan will be about 10 minutes using the GE Logiq E9 scanner and optionally the GE Logiq E10 scanner to measure the stiffness of liver (used as a benchmark reference in this study). The second ultrasound scan will be about 30 minutes using the Verasonics scanner. In the second scan, multiple miniature mechanical vibrators will be placed on the body surface of rib cage of the subject. An elastic strip (fibric covered neoprene) wrapped around the chest and secured by hook-and-loop will be used to hold the mini-vibrators in contact with body surface. Alternatively, mechanical vibrations are introduced by an audio loudspeaker in contact with the subject's upper torso. Or mechanical vibration will be introduced through a miniature vibrator attached to the ultrasound probe. An experienced sonographer from Mayo will image the liver with an ultrasound transducer. The best intercostal window that shows an area of the hepatic lobe away from the diaphragm and adjacent vessels will be chosen. Repeated stiffness measurements will be made at different locations within the liver parenchyma while the mini-vibrators introduce shear wave in the liver, similar to an MRE examination. The subject will be instructed to briefly hold his/her breath during each measurement. This procedure will take about 30 minutes. The study is non-invasive and imposes no discomfort to the subject. Liver MRE results will be obtained from the medical record of the patient and compared with ultrasound results. Most healthy volunteers will not have liver MRE examination and therefore liver stiffness measured by mechanical vibrations will be compared with those obtained with the GE Logiq E9 scanner. Some healthy volunteers may be offered liver MRE examination so that we can compare the ultrasound and MRE measurements in the healthy cohort. Other clinical information relevant to liver diseases if available, such as results of liver biopsy or liver function tests, will also be obtained from medical records to assist data analysis. If a healthy volunteer were found to have abnormal liver stiffness by MRE performed as part of this research study, we will inform the healthy volunteer, and if requested, to his/her primary care provider. We will not communicate with patients on their MRE results, as their MRE examinations are clinically indicated and they should be aware of their MRE results from their clinical care provider. Reliability of the new ultrasound technology used in this study for liver disease diagnosis is not established yet. Therefore, participants will not be informed of research ultrasound measurement results. Incidental findings in subjects if noted (e.g if splenomegaly, adenopathy, or a mass) will be communicated to the subject, and if requested, to his/her primary care provider.

In addition to liver stiffness data, un-processed ultrasound data from conventional B-mode ultrasound imaging will be collected and analyzed offline to estimate the liver fat content. Completely de-identified data may be shared with GE to see if more advanced GE processing can improve the outcome. Correlation of liver stiffness (reflecting fibrosis) and liver fat content (reflecting steatosis) will be analyzed. Information from the patients' medical record about the status of liver disease may be used to help interpreting the results. We may screen potential patient candidates' MRE results to help select patients to enroll for this study, to ensure that we have a relatively uniform distribution of patient population to cover the full spectrum of the disease.

Resources: *Describe the available resources to conduct the research (personnel, time, facilities, mentor commitment, etc.):*

This project will be funded by a NIH R01 grant. [name] (GI) and [name] (Radiology) are co-investigator of this project. We have commitments from all participating personnel and their efforts will be funded by the R01 grant.

Check all that apply. If none apply, leave blank:

This is a multisite study involving Mayo Clinic and non-Mayo Clinic sites.

When checked, describe the research procedures/activities being conducted **only** at Mayo Clinic:

Mayo Clinic staff will be engaged in research activity at a non-Mayo Clinic site. *When checked, provide the location and a detailed description of the Mayo Clinic research staff involvement.*

This study is to establish and/or maintain an ongoing database or registry for research purposes only.

The research involves contact or interaction with subjects, for example, surveys, questionnaires, observation, blood draw.

The study involves audiotaping or videotaping

Blood Collection

If this study involves prospective blood collection by finger, heel, ear stick or venipuncture, complete the following:

From healthy, non pregnant, adult subjects who weigh at least 110 pounds. For a minimal risk application, the amount of blood drawn from these subjects may not exceed 550ml in an 8 week period and collection may not occur more frequently than 2 times per week.

Volume per blood draw: _____ ml

Frequency of blood draw (e.g. single draw, time(s) per week, per year, etc.) _____

From other adults and children considering age, weight, and health of subject. For a minimal risk application, the amount of blood drawn from these subjects may not exceed the lesser of 50 ml or 3 ml per kg in an 8 week period, and collection may not occur more frequently than 2 times per week.

Volume per blood draw: _____ ml

Frequency of blood draw (e.g. single draw, time(s) per week, per year, etc.) _____

Review of Chart, Images, Specimens

Provide the date range for collection of data and/or specimens that will be included in your research dataset.
(Example: 01/01/2000 to 12/31/2012)

Date range: From 05 / 01 / 2013 to 05 / 01 / 2025

Check all that apply:

This study involves only data and/or specimens that exist at the time this application is submitted to the IRB (IRB submission date). No data or specimens will be collected beyond this date.

This study involves only data and/or specimens that will be collected after submission to the IRB.

The study involves data and/or specimens that exist at the time of submission to the IRB **and** data and/or specimens that will be collected after submission to the IRB, for example a study that includes collection of existing data and prospective collection of specimens.

Data and/or specimens used in this study are collected under another IRB protocol. *When checked, provide the IRB number(s) from which the research material will be obtained and check the box below to attest that subjects have provided consent for future use of their data and/or specimens, as described in this protocol.*

IRB Number(s):

Subjects have provided consent for use of their data and/or specimens, as described in this protocol.

Other data sources will be utilized in this study. When checked, provide all data sources:

Data Confidentiality, HIPAA Subject Identifiers

Review the list of subject identifiers below and, if applicable, check the box next to each subject identifier being recorded at the time you are collecting/abstracting data/specimens for use in this study.

Subject Identifiers: Individually identifiable information, including demographic data, that identifies the individual or for which there is reasonable basis to believe it can be used to identify the individual. NOTE: Identifiers apply to subjects enrolled in your study and to the subject's relatives, household members, employers, etc.

Internal refers to subject identifiers that will be included in the dataset maintained by the study team.

External refers to subject identifiers that will be shared with persons outside of the immediate study team, for example, sent to an external collaborator or shared with a national registry.

SUBJECT IDENTIFIERS Check all that apply	INTERNAL IDENTIFIER	EXTERNAL IDENTIFIER
Name	x	
Social Security number		
Medical record/patient registration number, lab accession, specimen or radiologic image number	x	
Study number, subject ID, or any other unique identifying number, characteristic or code that can be used to link the identity of the subject to the data	x	
Dates: All elements of dates [month, day, and year] directly related to an individual. Their birth date, date of death, date of diagnosis, etc. Note: Recording a year only is not a unique identifier.		
Medical device identifiers and serial numbers		
Biometric identifiers, including finger and voice prints, full face photographic images and any comparable images		
Web Universal Resource Locators (URLs), Internet Protocol (IP) address numbers, email address		
Street address, city, county, precinct, zip code, and their equivalent geocodes		
Phone or fax numbers		
Account, member, certificate or professional license numbers, health beneficiary numbers		
Vehicle identifiers and serial numbers, including license plate numbers		
If None of the above identifiers will be recorded or maintained in the dataset and/or sent outside of the study team, please check "None".	 None	 None

Statistical Information

Note: Power analyses and study endpoints are not needed for a pilot or feasibility studies.

No statistical information. *If checked, please explain:*

Statistical Considerations

Power Statement:

This protocol was initially approved as a pilot study to enroll 60 subjects to provide preliminary data for NIH grant applications. Our NIH R01 application is now funded. Therefore, we need to study 45 additional patients for Aim 2, and 220 patients for Aim 3 of the awarded NIH grant. Justification of sample size (45 and 220 patients) can be found in page 66-68 of the NIH application, which is attached to Section 47 (Supporting Documents) of this IRB application. Therefore, we will need to increase the target enrollment for this study by 265 (45+220) to meet the need of NIH award. This brings the total enrollment number to 325 (60+265).

Data Analysis Plan:

Detailed data analysis plan can be found in page 66-68 of the NIH application, which is attached to Section 47 (Supporting Documents) of this IRB application.

Endpoints

Primary: We study 325 subjects with successful MRE and ultrasound measurements.

Secondary: Some patients will have failed MRE or ultrasound measurements due to technical difficulties. We therefore will continue recruiting up to 400 subjects until we reach the primary end point.

Data Analysis Plan

Intraclass correlation coefficients (ICC) will be calculated from random effects models to evaluate the inter-sonographer agreement. For these models, subject and sonographer will both be included as random effects. The within subject variance components from the model will be used to obtain an estimate of the overall measurement variance for REVUE. In addition to the overall analysis, we will compare repeatability and reproducibility measures across subgroups defined according to subject BMI (<30 and ≥ 30) and perform supplemental analyses separately for each BMI category as appropriate. In all cases, findings will be presented using point estimates and 95% confidence intervals.

The primary objective is to demonstrate whether REVUE is an effective alternative to MRE for distinguishing patients with minimal fibrosis (MRE ≤ 2.9 kPa) and advanced fibrosis (MRE ≥ 5.0 kPa). To accomplish this objective, ROC curve analyses will be performed using logistic regression for these MRE cut points. Separate analyses will be performed to assess the performance of both REVUE and Aixplorer®. The results of these analyses will be summarized using the point estimate and 95% confidence interval for the area under the ROC curve (AUROC). In addition, we will compare the AUROC between ultrasound methods using the approach described by DeLong. Secondary analyses will be performed using Pearson product-moment correlation and linear regression to evaluate the association of REVUE and Aixplorer® measurements with MRE. The correlation coefficients obtained from these analyses will be summarized and compared (REVUE vs. Aixplorer®) using the method described in. To supplement the overall findings, we will repeat the analyses according to BMI (all BMI vs. $BMI \geq 30$) and, if appropriate, according to disease (chronic viral hepatitis and alcoholic/nonalcoholic fatty liver disease). In all cases, two-tailed p-values ≤ 0.05 will be considered statistically significant.

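### Ultrasound reliability, known only after the study scan, is an exclusion criterion and failures are replaced, so accuracy is conditional on scan success and no success proportion is planned

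*Combined protocol and SAP*

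**What the plan says.** Under Subject Information, the Exclusion Criteria list "subjects with unreliable ultrasound or MRE measurements" beside lack of capacity to consent and pregnancy. No threshold for reliability is given, and no device is named.

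Under Endpoints, the primary entry reads "We study 325 subjects with successful MRE and ultrasound measurements". The secondary entry states "Some patients will have failed MRE or ultrasound measurements due to technical difficulties" and continues "We therefore will continue recruiting up to 400 subjects until we reach the primary end point". That entry is a replacement rule; it does not plan to estimate how often scans fail.

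The Data Analysis Plan that follows Endpoints sets the primary objective as "whether REVUE is an effective alternative to MRE" for separating minimal from advanced fibrosis. It states "Separate analyses will be performed to assess the performance of both REVUE and Aixplorer" and "we will compare the AUROC between ultrasound methods using the approach described by DeLong", and adds correlation and regression against MRE. For precision it plans ICCs and variance components, and "we will compare repeatability and reproducibility measures across subgroups defined according to subject BMI".

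The shorter Data Analysis Plan entry under Statistical Considerations refers to pages 66-68 of the NIH application for the detailed plan. Those pages are not part of the document.

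**The concern.** An eligibility criterion should be decidable before the procedure under study. Here the index test is itself a study procedure, about 30 minutes on the Verasonics scanner (Study Design, Methods), so the criterion conditions on how that test performed. Followed as written, the exclusion and the replacement rule together remove failed scans from every planned result.

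This matters because of what the trial wants to claim. A patient whose scan fails gets no usable value, so whether REVUE can stand in for MRE depends on how often it yields a value as well as on accuracy when it does. The Background expects better penetration and more dependable measurements in obese patients and calls this an important advantage. Precision by BMI is analysed, but only from values that were obtained; how often a value is obtained is not analysed.

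The undefined label also leaves discretion. The Methods section allows candidates' MRE results to be seen before enrolment, so a judgement that a scan was unreliable could be made by someone who knows the reference result.

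**Working it through.** **1. The plan's own totals.** Power Statement: 60 (pilot) + 45 (Aim 2) + 220 (Aim 3) = 325. This reproduces. The 45 and 220 cannot be re-derived, because their justification is in the NIH application.

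**2. What the replacement rule allows.** Endpoints: 325 successes from at most 400 recruited.
- Maximum failures: 400 − 325 = 75.
- As a proportion: 75/400 = 18.75%.
- At 20% failure, 325/0.80 = 406.25, so 407 would be needed; 400 would yield 400 × 0.80 = 320.

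The 18.75% pools MRE and ultrasound failures. It is a ceiling set by the cap, not an expected rate for either method.

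**3. When reliability is known.** The Exclusion Criteria treat it as an eligibility matter. Under Methods, the research ultrasound is performed after enrolment, so its reliability cannot be known at eligibility. The timing point is weaker for MRE, which is clinically indicated in patients and may be screened beforehand. The finding therefore concerns ultrasound.

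**4. What each planned analysis can see.**
- AUROC for each device: subjects with valid MRE and a value from that device. The text does not say whether failure of one device removes the subject from both analyses.
- DeLong comparison of paired curves: subjects with valid MRE and values from both devices.
- Correlation and regression with MRE: values obtained.
- ICC, variance components, and repeatability and reproducibility by BMI: values obtained.

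None has attempted scans as its denominator.

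**5. What a success proportion would show.** Failure rates here are assumptions, since the document gives none.
- Joint success (exact 95% CI): if 400 are recruited for 325 successes, 325/400 = 81.25% (77.1 to 85.0%). If 362 are needed, 325/362 = 89.8% (86.2 to 92.7%).
- Failure for one device, taking Aim 3 as an example (Wilson 95% CI): 11/220 = 5.0% (2.8 to 8.7%); 22/220 = 10.0% (6.7 to 14.7%). In a BMI group assumed to hold half of these, 11/110 = 10.0% (5.7 to 17.0%).
- These denominators treat 220 as the number of attempts. If 220 must succeed, attempts would be about 220/0.95 ≈ 232 at 5% failure or 220/0.90 ≈ 244 at 10%. The intervals change little: 24/244 = 9.8% (6.7 to 14.2%).

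The existing scans would thus estimate overall success usefully and BMI-specific success more coarsely.

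**The case against.** **The detailed plan is elsewhere.** NIH application pages 66-68 may define reliability and plan a success-rate analysis. This stands as a limit: a reader might infer that no such analysis exists anywhere, and the document does not support that. Those pages would not, however, correct the exclusion criterion, which is in the protocol itself.

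**The planned estimand is legitimate.** Accuracy when a value is obtained is a proper question, and the stated hypothesis is correlation with MRE. This also stands. A reader might infer that the AUROC is biased or the primary analysis invalid; neither follows. Nor can one say that the contrast between REVUE and its comparator is inflated, because failures may affect either device and the direction is unknown.

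**The AUROC can be made to fall.** Scoring 0.5 for every pair with a failed scan, with failure unrelated to disease, takes an assumed 0.90 to 0.5 + 0.95² × 0.40 = 0.861 at 5% failure and 0.5 + 0.90² × 0.40 = 0.824 at 10%. A reader might take this as the size of the problem. It comes wholly from the scoring rule, which nothing in the document supports, since a recognised failure could instead lead to a repeat scan or to MRE. It is not evidence of magnitude.

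**Precision by BMI is already planned.** True, but it answers a different question from how often a usable value is obtained.

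**Patients may be selected on MRE result.** Methods allows this to give a fairly even spread of disease, so a success rate from this sample need not reflect ordinary referrals. This stands and should be stated with the rate.

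**A test between devices would be weak.** With independent failures at 5% versus 10%, McNemar power is about 51% at n = 220 and 29% at n = 110 (44% and 21% with the exact test). That argues for estimates with CIs and leaves the test optional.

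**Conclusion.** The concern holds in a limited form. It rests on a stated rule rather than on missing detail alone: the exclusion depends on the result of the index scan, and failures are replaced. As written, all accuracy and agreement results are conditional on scan success, and this text plans no success proportion by device or BMI. The complete-case AUROC remains valid for what it measures, but it cannot by itself support the claim that REVUE is an effective alternative to MRE or the expected benefit in obese patients.

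The size of any overstatement is unknown, because no failure rate is given. The only documented bound is the pooled ceiling of 75 failures in 400 (18.75%), and it applies only if 325 is to be reached. A reader might infer that unreliability will be used selectively to favour REVUE. The document shows only that the label is undefined and could be applied with the MRE result known.

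This should be fixed. Confidence is medium because of the unseen NIH pages.

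**What to change.** 1. Reconcile the comparator, so that per-device reporting has a meaning: the Data Analysis Plan names Aixplorer, while Methods names the GE Logiq E9 and optionally the E10. Since Methods allows three ways of introducing vibration, also say what counts as one attempted REVUE scan.
2. Remove unreliable ultrasound from the exclusion criteria. Define reliability per device in advance, without reference to the MRE result, and record it as an outcome for every attempted scan.
3. Keep the complete-case AUROC and the DeLong comparison as the main accuracy analysis. State that it is conditional on valid MRE and reliable values from both devices.
4. Beside it, report the success count and proportion with 95% CI per device among all subjects with an attempted scan, not only the 325 successes. Do this overall and for BMI <30 and ≥30, to be read as estimates.
5. State as a limit that patients may be selected by MRE result, so the rates need not carry over to ordinary referrals.

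The 325/400 recruitment rule can stay. A sensitivity AUROC that counts failed scans and a McNemar comparison are optional. If the NIH pages already contain a reliability definition or success-rate analysis, bring it into this text.

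Cost: protocol and analysis wording, a little more recording and a little more analysis. No scans or subjects are added, because the failed scans are performed anyway. The results may give a less favourable picture of REVUE.

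### The inter-sonographer ICC model names no subject-by-sonographer effect; if crossed replicate readings are modelled, the ICC would be somewhat too high and the REVUE measurement variance too low

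*Combined protocol and SAP*

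**What the plan says.** The last Data Analysis Plan section of the combined protocol and SAP gives the purpose of the model: "Intraclass correlation coefficients (ICC) will be calculated from random effects models to evaluate the inter-sonographer agreement". It then names two random effects: "For these models, subject and sonographer will both be included as random effects". The output has a second use: "The within subject variance components from the model will be used to obtain an estimate of the overall measurement variance for REVUE". The section adds that "we will compare repeatability and reproducibility measures across subgroups defined according to subject BMI", with the split at 30, and that results are reported as point estimates with 95% confidence intervals. No target or threshold for the ICC is given.

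On data collection, Methods (Study Design) says: "An experienced sonographer from Mayo will image the liver with an ultrasound transducer". It also says: "The best intercostal window that shows an area of the hepatic lobe away from the diaphragm and adjacent vessels will be chosen". On replication: "Repeated stiffness measurements will be made at different locations within the liver parenchyma".

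The documents do not state how many sonographers scan each subject, how many readings each takes, whether readings or a summary value enter the model, or which form of ICC is meant. A reference elsewhere in the plan covers some of this: "Detailed data analysis plan can be found in page 66-68 of the NIH application". Those pages are not among the documents supplied.

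**The concern.** An inter-sonographer ICC needs at least some subjects scanned by more than one sonographer. Repeatability reported beside reproducibility, together with repeated readings in Methods, points to replicate-level data. In such a design there are four sources of variation: subject, sonographer, subject-by-sonographer (one operator reads a given patient differently from another operator, beyond a constant shift) and residual. An intercostal window has to be chosen for the scan, so operator-by-patient variation is plausible. Its size is not documented.

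If that component exists and has no term of its own, the fit must place it elsewhere. Readings by the same sonographer on the same subject share it, so part of it looks like a difference between subjects and most of the rest goes to the residual. Agreement between operators is then overstated, REVUE measurement variance is understated, and the residual no longer isolates repeatability. What is at stake is a secondary, descriptive result on reliability, and the BMI comparison built on it.

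**Working it through.** **Inputs.** From the documents: the two named random effects and the use of the within-subject components. The documents give no variance components, number of sonographers (k) or repeats (m), so these are assumed: Vs = 1 (subject), Vr = 0.02 (sonographer), Ve = 0.10 (residual), interaction Vi from 0 to 0.20, k = 2 to 4, m = 2 to 10. The number of subjects is set at n = 45, the Aim 2 figure in the Power Statement. That Aim 2 is the reproducibility study is also an assumption. The plan states no ICC, so there is no figure to reproduce.

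**Formulas** (balanced crossed design, expected mean squares, interaction pooled with error):

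- f = m(n−1)(k−1) / (nkm − n − k + 1)
- residual estimates Ve + f·Vi
- subject component estimates Vs + Vi(m−f)/(km)
- sonographer component estimates Vr + Vi(m−f)/(nm)
- true single-reading ICC = Vs/(Vs+Vr+Vi+Ve); true measurement variance = Vr+Vi+Ve

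**Worked case**, n = 45, k = 2, m = 10, Vi = 0.10:

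- f = 440/854 = 0.515
- residual 0.10 + 0.0515 = 0.152 (true 0.10)
- subject 1 + 0.10 × 9.485/20 = 1.047 (true 1)
- sonographer 0.02 + 0.10 × 9.485/450 = 0.022 (true 0.02)
- measurement variance 0.174, against 0.220
- ICC 1.047/1.221 = 0.858, against 1/1.22 = 0.820

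**Over the grid** (n = 45):

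| Vi | True ICC | Two-effect ICC, k = 2, m = 10 | ICC bias, k = 2–4, m = 2–10 |
|---|---|---|---|
| 0 | 0.893 | 0.893 | 0 |
| 0.02 | 0.877 | 0.885 | 0.0025–0.008 |
| 0.05 | 0.855 | 0.875 | 0.006–0.020 |
| 0.10 | 0.820 | 0.858 | 0.012–0.038 |
| 0.20 | 0.758 | 0.828 | 0.022–0.071 |

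The bias is largest with 2 sonographers and 10 repeats and smallest with 4 sonographers and 2 repeats.

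**Against sampling error.** In simulation (n = 45, k = 2, m = 10) the SD of the two-effect ICC is about 0.033 at Vi = 0.02 and 0.036 at 0.10. The bias is thus about a quarter of an SD (0.008/0.033) and about one SD (0.038/0.036).

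**When it vanishes.** If Vi = 0 every extra term is zero. If m = 1, then f = 1 and m − f = 0, so the residual absorbs the whole interaction and the ICC is right for the unit analysed. For example, with the mean of 10 readings and Vi = 0.10, the target is 1/(1 + 0.02 + 0.10 + 0.01) = 0.885, which is correct for a mean of 10.

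**Other variances.** With Vs = 1, Vr = 0.05, Vi = 0.10, Ve = 0.15, n = 45, k = 2, m = 5, the ICC is 0.803 against 0.769 and the measurement variance 0.256 against 0.300, about 15% low. The direction held in all of 200,000 random parameter sets with m ≥ 2 and Vi > 0.

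**BMI comparison.** Assume Vi = 0.05 below BMI 30 and 0.20 at or above it. The true ICC difference is 0.855 − 0.758 = 0.097. The two-effect model hides 0.051 of it at k = 2, m = 10 and 0.015 at k = 4, m = 2. With 22 subjects per group (45 split about evenly, an assumption), the simulated SD of the two-effect ICC difference is about 0.075 and 0.081. The hidden part is therefore about 0.7 SD and 0.2 SD. For a milder contrast (0.02 against 0.05), 0.004 to 0.012 is hidden against an SD of about 0.06.

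**The case against.** The strongest reply is that this is a summary and not the full plan. The grant pages are cited for the detail and may give the sonographers per subject, the repeats, the unit of analysis and an interaction term. The sentence in question says that two effects are included; it does not say that nothing else is. The reference to within-subject components in the plural fits two terms or three. All of this stands. A reader might infer that the plan excludes the interaction and so contains a proven error, but the documents support only that the term is not named. The section does, however, set out a concrete model, and following it as written with crossed replicates would give the bias shown.

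Three other stronger readings are tempting and do not hold.

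- That the model would conceal a real BMI difference. As a share, up to about half of an assumed ICC difference is hidden (0.051 of 0.097), but this is under one SD of the comparison even for that wide contrast.
- That the Background's expectation of more reliable readings in obese patients is at risk. That sentence compares the new method with existing ultrasound techniques, not BMI groups within REVUE.
- That Methods contradicts the ICC analysis by mentioning one sonographer. The wording can simply describe a single scan. It leaves the design unstated.

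It is also fair that no decision rule or primary result depends on the ICC.

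**Conclusion.** The concern holds as a conditional weakness in the stated model. It requires crossed sonographers, replicate-level modelling and interaction variance above zero. The first two are suggested by the text and the third is plausible; none is stated. Under these conditions the direction is certain: ICC too high, measurement variance too low, residual too large for repeatability. The size is illustrative because every variance component is assumed. On the grid above it runs from negligible against sampling error at interaction 0.02 to about one SD of the ICC estimate at 0.10 in the least favourable layout (2 sonographers, 10 repeats, 45 subjects). Any distortion of the BMI comparison is smaller than its sampling error, and the AUROC analysis is unaffected. This is a cheap improvement to a secondary analysis; it does not threaten the study's main conclusion.

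**What to change.** State how many sonographers scan each subject, how many readings each takes, and whether readings or one summary value per subject and sonographer enter the model. If the grant pages already say so, carry it into this section. Then, according to the design:

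- **Crossed sonographers, replicates modelled.** Add a subject-by-sonographer random effect. Define ICC = subject / (subject + sonographer + interaction + residual) and REVUE measurement variance = sonographer + interaction + residual. Report the residual as within-examination variation, noting that it includes differences between liver locations because the readings are taken at different sites.
- **One summary value per subject and sonographer.** Keep the two-effect model, say so, and compute within-examination variation separately with the same note.
- **One sonographer per subject.** Report within-examination variation only, and drop the inter-sonographer and reproducibility claims.

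If crossed replicate scans are already planned, the cost is one model term and a sentence, with no extra scans. The statistical price is a lower ICC and a wider interval: in simulation with 45 subjects, 2 sonographers, 10 repeats and interaction 0.10, the SD of the ICC rises from about 0.036 to about 0.045. With 22 subjects per BMI group, the same layout and the assumed contrast of 0.05 against 0.20, the SD of the BMI difference rises from about 0.075 to about 0.10.
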